6.2.4.4. Analysis Excluding US/Korea Non-Dual Refractory Males

Given the restriction in the US/Korea of only allowing dual refractory males to receive filgotinib 200 mg, there exists an inherent imbalance in the Cohort B Induction Study between subjects randomized to filgotinib 200 mg and the placebo group with respect to US/Korea non-dual refractory males who will be present in the placebo group, but not in the filgotinib 200 mg group. Recognizing this imbalance and the theoretical potential for non-dual refractory subjects to have better disease prognosis and a higher chance of response, a sensitivity analysis excluding US/Korea non-dual refractory males from the placebo group in the FAS for Cohort B Induction Study will be conducted using the stratified CMH test for the treatment comparison between the filgotinib 200 mg and the placebo group on EBS remission at Week 10. This analysis will be the primary analysis for evaluating the efficacy of the filgotinib 200 mg dose group in the Cohort B Induction Study in support of a Japanese marketing application.

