#### **Treatment Regimen (Cohorts A and B Induction Studies)**

Based on protocol eligibility criteria, subjects will be screened for enrollment in *either* Cohort A or Cohort B.

Subjects who meet protocol eligibility criteria will be assigned to the respective Cohort and subsequently randomized in a blinded fashion in a 2:2:1 ratio to 1 of 3 treatments as follows:

**Treatment Group 1 (n = 260):** filgotinib 200 mg and placebo-to-match (PTM) filgotinib 100 mg, once daily

**Treatment Group 2 (n = 260):** filgotinib 100 mg and PTM filgotinib 200 mg, once daily

**Treatment Group 3 (n = 130):** PTM filgotinib 200 mg and PTM filgotinib 100 mg, once daily

Note: United States (US) and Korea males who have not failed at least 2 biologic therapies (any tumor necrosis factor-alpha [TNF $\alpha$ ] antagonist and vedolizumab) will be randomized in a 2:1 ratio to either filgotinib 100 mg or matching placebo.

Within each Cohort, treatment assignments will be stratified according to the following factors in the Induction and Maintenance studies:

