### 1.4. Risk/Benefit Assessment for the Study

Ulcerative colitis is a progressive and potentially life-threatening disease with few treatment options, many of which result in primary or secondary nonresponse. Inflammatory bowel disease may lead to increased risk of gastrointestinal malignancies, impairment in quality of life, and ultimate need for life-altering surgery. Current treatment options are limited in ability to establish mucosal healing and clinical remission and have significant safety and efficacy limitations; for example, biologics have significant immunogenic risks and steroids are associated with increased morbidity and mortality. Remission rates are generally low when compared to placebo rates across most therapies for IBD. There remains substantial unmet need in IBD, particularly in moderate to severe disease. The lifelong nature of IBD increases the probability that subjects have cycled through various therapies, leaving few approved options.

Nonclinical studies in rats and dogs identified lymphoid tissues and testes as target organs for filgotinib in long-term repeat-dose toxicity studies. Although decreased lymphocyte numbers observed in nonclinical studies have not been seen in clinical studies, hematological assessment will be performed throughout the present study to ensure this potential risk is appropriately monitored. In both rats and dogs, microscopic findings in the testes included germ cell depletion and degeneration, with reduced sperm content and increased cell debris in the epididymis and reduction in fertility in male rats. The dog was determined to be the most sensitive species. When using the AUC at the NOAELs for dogs in the 26-week and 39-week chronic toxicity studies, and the 39-week targeted exposure toxicity study, the exposure margins compared with the highest proposed clinical dose of 200 mg once daily are 2.5, 1.9, and 3.6-fold respectively, in subjects with CD. A male safety study is planned to examine the potential effect of filgotinib on sperm/ejaculate parameters. Pending those results, the use of 200 mg in males in the US and Korea with CD or UC will be limited to subjects who have failed at least 2 biologic therapies (any TNF $\alpha$  antagonist and vedolizumab). Refer to the IB for further information about nonclinical and clinical testicular findings.

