#### Treatment Groups (Induction Study)

**Treatment Group 1 (n = 260):** filgotinib 200 mg and placebo-to-match (PTM) filgotinib 100 mg, once daily

**Treatment Group 2 (n = 260):** filgotinib 100 mg and PTM filgotinib 200 mg, once daily

**Treatment Group 3 (n = 130):** PTM filgotinib 200 mg and PTM filgotinib 100 mg, once daily

Note: US and Korea males who have not failed at least two biologic therapies (any TNF $\alpha$  antagonist and vedolizumab) will be randomized in a 2:1 ratio to either filgotinib 100 mg or matching placebo.

Within each Cohort, treatment assignments will be stratified according to the following factors in the Induction and Maintenance studies:

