### 6.1. Subject Enrollment and Treatment Assignment

Based on protocol eligibility criteria, subjects will be screened for enrollment in *either* Cohort A or Cohort B.

Subjects who meet the protocol criteria will be assigned to the respective cohort and subsequently randomized in a blinded fashion in a 2:2:1 ratio to 1 of 3 treatments as follows:

- **Treatment 1 (n = 260):** filgotinib 200 mg and PTM filgotinib 100 mg, once daily
- **Treatment 2 (n = 260):** filgotinib 100 mg and PTM filgotinib 200 mg, once daily
- **Treatment 3 (n = 130):** PTM filgotinib 200 mg and PTM filgotinib 100 mg, once daily

Note: US and Korea males who have not failed at least two biologic regimens (any TNF $\alpha$  antagonist and vedolizumab) will be randomized in a 2:1 ratio to either filgotinib 100 mg or matching placebo.

Within each Cohort, treatment assignments will be stratified according to the following factors in the Induction and Maintenance studies:

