3.3. Strata and Covariates

Subjects will be randomly assigned to treatment groups via the interactive web response system (IWRS) using a stratified randomization schedule into each individual study (Cohort A Induction Study, Cohort B Induction Study, and Maintenance Study). Details of the randomization ratio and stratification variables for each study are provided in Section 1.2.

If there are discrepancies in stratification factor values between the IWRS and the clinical database, the baseline values recorded in the clinical database will be used for analyses. For deriving concomitant medication use at Day 1, the start date of such medication should be before or on the same date of the first dose of study drug and with either the stop date of such medication being on or after the first dose of study drug or with ‘ongoing’ status.

Stratification factors will be used as covariates in evaluating efficacy endpoints, as specified in Section 6.

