5.2. Baseline Disease Characteristics

For the Induction Studies (Cohort A Induction Study and Cohort B Induction Study), Cohorts A and B Induction Studies combined, and Maintenance Study, the following baseline disease characteristics will be summarized using Safety Analysis Sets by the same grouping as the demographic tables, using descriptive statistics for continuous variables, and using number and percentage of subjects for categorical variable:

- Duration of UC (in years) from date of diagnosis to first dosing date
- Duration of UC (< 1 year, ≥ 1 and < 3 years, ≥ 3 and < 7 years, ≥ 7 years)

- Have a history of pancolitis (yes, no, unknown)
- MCS score (Induction studies only)
- MCS score (≤ 8 , ≥ 9) (Induction studies only)
- Partial MCS score (Induction studies only)
- Endoscopic subscore of 3 (yes, no) (Induction studies only)
- Participation in Cohort A or Cohort B (Maintenance Study Only)
- Fecal calprotectin ($\mu\text{g/g}$) (re-baseline value for Maintenance Study)
- Fecal calprotectin ($\leq 250 \mu\text{g/g}$, $> 250 \mu\text{g/g}$) (Induction studies only)
- hs-CRP (mg/L) (re-baseline value for Maintenance Study)
- hs-CRP ($\leq 3 \text{ mg/L}$, $> 3 \text{ mg/L}$) (Induction studies only)
- UC treatment history

Prior use of systemic corticosteroids (yes, no)

Prior use of immunomodulators (yes, no)

Number of prior exposure to biologic agent listed in [Appendix 2](#) (0, 1, 2, ≥ 3)

Prior use of TNF α antagonist listed in [Appendix 2](#) (yes, no; for Cohort B Induction Study and Cohorts A and B Induction Studies combined) and for subjects with prior use:

■ Number of TNF α antagonist used

- 1
- 2
- ≥ 3

■ Worst outcome of prior use of TNF α antagonist

- Treatment failure
- Intolerance, including both allergic and non-allergic intolerance
- Other

Prior use of vedolizumab (yes, no; for Cohort B Induction Study and Cohorts A and B Induction Studies combined) and for subjects with prior use:

- Worst outcome of prior use of vedolizumab
 - Treatment failure
 - Intolerance, including both allergic and non-allergic intolerance
 - Other

Prior use of both TNF α antagonist and vedolizumab (yes, no; for Cohort B Induction Study and Cohorts A and B Induction Studies combined)

Note: The worst outcome of a prior treatment is treatment failure, followed by intolerance, and then other outcomes.

Prior failure of both TNF-alpha antagonist and vedolizumab (for Cohort B Induction Study and Cohorts A and B Induction Studies combined)

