- Yes (dual refractory, defined as those who have failed at least 2 classes of biologic therapies [any TNF α antagonist and vedolizumab])
 - US/Korea Males
 - Subjects other than US/Korea Males
- No
 - US/Korea Males
 - Subjects other than US/Korea Males
- Corticosteroid and Immunomodulator Treatment at baseline (at re-baseline for Maintenance Study)

Concomitant use of systemically absorbed corticosteroids and/or immunomodulator at baseline/re-baseline, including: a) systemically absorbed corticosteroids only, b) immunomodulators only, c) both, and d) neither;

Prednisone equivalent dose for subjects who are on systemically absorbed corticosteroids at baseline/re-baseline (mg/day)

Prednisone equivalent dose for subjects who are on systemically absorbed corticosteroids at baseline/re-baseline (> 0 to 10 mg/day, > 10 to 20 mg/day, > 20 mg/day)

5-aminosalicylates (yes, no)

In addition, another baseline disease characteristics table for Maintenance Study using the FAS will be generated, including the above baseline characteristics except those marked as “Induction studies only” and the following additional variables:

- MCS score at re-baseline
- MCS score at re-baseline (≤ 8 , ≥ 9)
- Partial MCS score at re-baseline
- Endoscopic subscore of 3 at week 10 (yes, no)
- Fecal calprotectin at re-baseline (≤ 250 $\mu\text{g/g}$, > 250 $\mu\text{g/g}$)
- hs-CRP at re-baseline (≤ 3 mg/L , > 3 mg/L)
- EBS remission at Week 10 (yes, no)
- MCS remission at Week 10 (yes, no)
- Endoscopic subscore of 0 at Week 10 (yes, no)
- Geboes histologic remission at Week 10 (yes, no)

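### SAP 6.2.4.4 restores balance for 200 mg in Cohort B only if the dual-refractory category matches the scheme each US/Korea man was randomised under; select by scheme instead

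*SAP*

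**What the plan says.** Most subjects are randomised 2:2:1 to 200 mg, 100 mg or placebo. Protocol 3.3 sends "US and Korea males who have not failed at least two biologic therapies" to a 2:1 randomisation between 100 mg and placebo. Protocol 6.1 states the same rule for "US and Korea males who have not failed at least two biologic regimens", and SAP 1.2.1 also speaks of regimens. Protocol 1.4 gives the background: pending a male safety study, 200 mg in US and Korean men "will be limited to subjects who have failed at least 2 biologic therapies". Each version adds the same parenthesis, naming any TNF antagonist and vedolizumab.

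SAP 5.2 describes the yes category of prior failure of both as "dual refractory, defined as those who have failed at least 2 classes of biologic therapies", with the same parenthesis. The same section records the worst outcome of each prior treatment, listing treatment failure, then "Intolerance, including both allergic and non-allergic intolerance", then other outcomes. Cohort B entry (Protocol 4.4.1) accepts inadequate response, loss of response or intolerance.

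SAP 6.2.4.4 equates the US/Korea restriction with dual-refractory status and states that the non-dual refractory men will be in placebo but not on 200 mg. It then plans "a sensitivity analysis excluding US/Korea non-dual refractory males from the placebo group in the FAS for Cohort B Induction Study", comparing 200 mg with placebo by the stratified CMH test. It notes that non-dual refractory subjects may have a better prognosis. It names no data source for the status.

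**The concern.** The exclusion is meant to leave only subjects who could have been assigned 200 mg, so that the comparison is randomised again. What determines that chance is the scheme, 2:2:1 or 2:1. The analysis instead selects on a treatment-history category and applies it to one arm, relying on the premise that the other arm contains no such men.

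That premise needs two classifications to agree: the one made at randomisation and the one derived for SAP 5.2. Neither document says what counts as failure. A man who failed a TNF antagonist and did not tolerate vedolizumab might be treated as having failed both when the scheme was chosen, yet be recorded as intolerant of one in the derived history. He would be eligible for 200 mg and also non-dual refractory in the analysis.

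For most purposes this is a sensitivity analysis. For the Japanese application it carries the efficacy claim for 200 mg in Cohort B, so its analysis set should not rest on an unchecked premise.

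**Working it through.** **1. The plan's own figure.** Protocol 8.9.1 gives 90% power for 130 placebo and 260 per dose, 10% against 25%, two-sided 0.025.

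- Pooled rate: (130 × 0.10 + 260 × 0.25) / 390 = 0.20.
- Null SE: √(0.20 × 0.80 × (1/130 + 1/260)) = 0.0430.
- Alternative SE: √(0.10 × 0.90/130 + 0.25 × 0.75/260) = 0.0376.
- Continuity correction: 0.5 × (1/130 + 1/260) = 0.0058.
- Power: Φ((0.15 − 0.0058 − 2.241 × 0.0430) / 0.0376) = 0.899. Without the correction it is 0.923.

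The stated 90% reproduces.

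**2. The imbalance that 6.2.4.4 is meant to remove.** Let a share f of the 650 be restricted men. The documents do not give f. The 200 mg arm is then 0.4 × 650(1 − f), and placebo is 0.2 × 650(1 − f) + 650f/3.

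| f (assumed) | 200 mg | Placebo | Restricted men in placebo |
|---|---|---|---|
| 5% | 247 | 134 | 10.8 (8%) |
| 10% | 234 | 139 | 21.7 (16%) |
| 20% | 208 | 147 | 43.3 (29%) |

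The analysis addresses a real problem.

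**3. What the planned rule does to each kind of US/Korea man.**

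| Scheme used | SAP category | 200 mg arm | Placebo arm | Effect |
|---|---|---|---|---|
| 2:2:1 | Dual refractory | Kept | Kept | Balanced |
| 2:2:1 | Not dual refractory | Kept | Removed | New imbalance |
| 2:1 | Not dual refractory | None exist | Removed | As intended |
| 2:1 | Dual refractory | None exist | Kept | No 200 mg counterpart |

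Rows 2 and 4 are empty if the two classifications agree.

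**4. Size of row 2.** Let h be the share of the 200 mg arm in row 2, and g their excess remission rate. The documents give neither; I assume h = 2–10% and g = 5–10 points. With no drug effect and a remission rate p in everyone else, the 200 mg rate is p + h × g. The placebo rate after exclusion is p, so the bias is h × g.

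- Smallest: 0.02 × 0.05 = 0.001, or 0.1 points.
- Largest: 0.10 × 0.10 = 0.010, or 1.0 point.
- Men kept on 200 mg: 260 × h = 5 to 26.
- Placebo subjects removed although randomised 2:2:1: 130 × h = 2.6 to 13.

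Type I error was approximated without stratification, with p = 10%, 260 against 130(1 − h), and level 0.02499. It stays near 0.025 for h = 2%, is 0.025 to 0.026 for h = 5%, and 0.025 to 0.029 for h = 10%. Outside the assumed range, h = 10% with a 20-point gap gives 2.0 points and about 0.044. With h = 0, the bias is zero.

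**5. Row 4.** Its effect depends on how these men fare relative to the other placebo subjects, on which the documents are silent. No figure is attempted.

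**The case against.** The strongest reply is that all the wordings express one rule. A reader might infer from therapies, regimens and classes that two failed TNF antagonists would qualify a man for 200 mg in one place and not in another. The documents do not support that reading: the shared parenthesis joins any TNF antagonist and vedolizumab, and allowing two TNF antagonists would leave the mention of vedolizumab with no work to do. SAP 6.2.4.4 adopts the one-of-each reading. On that reading, with failure understood alike throughout, excluding from placebo alone and excluding from both arms select the same subjects.

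Nor do the documents show sites applying different rules; assignment comes through IWRS (Protocol 6.3.1, SAP 3.3). The variant in Protocol 5.3 concerns the open-label dose offered after disease worsening, not randomisation. SAP 3.3 does say that "the baseline values recorded in the clinical database will be used for analyses", but only for discrepant stratification factors, and dual-refractory status is not one. It would be wrong to infer that the category is known to come from the clinical database.

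The failure/intolerance split in SAP 5.2 is a descriptive summary, and the definition there does not say that intolerance is excluded. Planned outputs would also expose part of any problem: SAP 5.2 tabulates the category by US/Korea male status and treatment group, and SAP 6.2.5 has a matching subgroup.

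All of this stands, and it limits the point. It does not remove it. Failure remains undefined whichever noun is used. The planned tables would reveal row 2 but not row 4, because they do not cross the category with the scheme. And SAP 6.2.4.4 does not say what happens if such men are found on 200 mg.

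**Conclusion.** The point holds as a conditional weakness in how the analysis set is defined. SAP 6.2.4.4 is correct if dual-refractory status in SAP 5.2 coincides with the status used to choose the scheme, and nothing in the analysis secures or checks that. A reader might go further and conclude that the exclusion does create a bias, or that men were misclassified. The documents show neither.

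The size is unknown and probably small: 0.1 to 1.0 points against a design difference of 15, on an assumed share of 2–10% and gap of 5–10 points, and zero if the definitions match. The direction in favour of 200 mg rests on the SAP's own supposition of better prognosis. The main Cohort B analysis on the full analysis set does not use this exclusion. The matter deserves attention because this analysis is primary for one application and the remedy costs almost nothing.

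**What to change.** In SAP 6.2.4.4, define the set for both arms by the scheme recorded at assignment: keep every Cohort B FAS subject randomised 2:2:1 and exclude every subject randomised under the restricted 2:1 scheme. Report, by arm, how many subjects have a scheme that disagrees with the SAP dual-refractory category.

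Nobody assigned 200 mg is lost, since the 2:1 scheme does not offer that dose. If the definitions match, the set is the one already planned and there is no extra loss of power. If they do not, both kinds of error disappear by construction.

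The cost is a sentence or two and one count. The documents do not describe a separate 2:1 list, but IWRS makes the assignments and so should hold the scheme. No new data are needed.

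Separately, reconcile the wording of the restriction in the Protocol synopsis, 1.4, 3.3, 5.3 and 6.1 and in SAP 1.2.1 and 5.2, including whether intolerance counts as failure. Which rule is right is for the sponsor to settle; no view is taken here.

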6.2.5. Subgroup Analysis of the Primary Efficacy Endpoint

The following subgroup analyses will be performed for the primary efficacy endpoints for each individual study (Cohort A Induction Study, Cohort B Induction Study, and Maintenance Study):

Subgroups based on study stratification include:

Cohort A Induction Study Stratification Factors:

- Concomitant use of oral, systemically absorbed corticosteroids at Day 1 (yes, no)
- Concomitant use of immunomodulators at Day 1 (yes, no)

Cohort B Induction Study Stratification Factors:

- Exposure to biologic agent listed in [Appendix 2](#) (≤ 1 , > 1)
- Concomitant use of oral, systemically absorbed corticosteroids at Day 1 (yes, no)
- Concomitant use of immunomodulators at Day 1 (yes, no)

Maintenance Study Stratification Factors:

- Participation in Cohort A or Cohort B
- Concomitant use of oral, systemically absorbed corticosteroids at re-baseline (yes, no)
- Concomitant use of immunomodulators at re-baseline (yes, no)

Other subgroups for each individual study include:

- Age group on the date of first dose of the study drug (< 65 years, ≥ 65 years)
- Sex at birth (female, male)
- Race (Asian, Black or African American, White, and Other)
- Geographic region (the United States [US], non-US)
- Induction baseline hs-CRP (≤ 3 mg/L, > 3 mg/L)
- Induction baseline fecal calprotectin (≤ 250 µg/g, > 250 µg/g)
- Duration of UC (years from date diagnosed to first dose date of Induction study drug) (< 1 year, ≥ 1 to < 3 years, ≥ 3 to < 7 years, ≥ 7 years)
- Baseline disease activity (based on screening MCS) (6-8, 9-12)
- Previous exposure to TNFα antagonist (yes, no) (only for Cohort B Induction Study and Maintenance Study)
- Prior TNFα antagonist failure (yes, no) (only for Cohort B Induction Study and Maintenance Study)
- Previous exposure to vedolizumab (yes, no) (only for Cohort B Induction Study and Maintenance Study)
- Prior vedolizumab failure (yes, no) (only for Cohort B Induction Study and Maintenance Study)
- Dual refractory (yes, no) (only for Cohort B Induction Study and Maintenance Study)
- The following 4 subgroups (only for Cohort B Induction Study and Maintenance Study)
 - US/Korea males who are dual refractory
 - US/Korea males who are not dual refractory
 - Non-US/Korea males (US/Korea females and subjects from countries other than US and Korea) who are dual refractory
 - Non-US/Korea males who are not dual refractory

For a subject, if the value of the grouping variable cannot be determined, this subject will be excluded from the corresponding subgroup analysis. Non-stratified risk difference between treatment groups will be evaluated for each of the subgroups using Fisher's exact test. A forest plot will graphically present the non-stratified risk difference and 95% CI using normal approximation with a continuity correction on the treatment differences (filgotinib placebo) in EBS remission rates for each of the subgroups.

Additional subgroup analyses for geographic region may be added based on the distribution of study enrollment prior to study unblinding.

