1.3. Sample Size and Power

Induction Studies (Cohort A Induction Study and Cohort B Induction Study)

The sample size was chosen to ensure that a clinically meaningful difference in EBS remission rate at Week 10 could be detected when comparing filgotinib to placebo within each Induction Study. A sample size of 130 subjects in the placebo group and 260 subjects in each filgotinib dose (200 mg or 100 mg) group (N = 650 per cohort) will provide 90% power for each filgotinib dose group comparison to placebo at a 2-sided 0.025 significance level to detect a treatment difference in EBS remission rate of 15% (25% on filgotinib and 10% on placebo).

Maintenance Study

Assuming an induction response rate (ie, proportion of subjects achieving either EBS remission or MCS response at Week 10) of 55% among subjects receiving filgotinib 200 mg or 100 mg treatment, approximately 285 subjects from each filgotinib dose group from Cohorts A and B Induction Studies combined would be eligible to be re-randomized into the Maintenance Study.

The sample size was chosen to ensure that a clinically meaningful difference in EBS remission rate at Week 58 could be detected when comparing each filgotinib dose group (200 mg or 100 mg) to placebo in the Maintenance Study. A sample size of 95 subjects in the placebo group and 190 subjects in the filgotinib group at the same dose level as the induction dose will provide more than 85% power for each filgotinib dose group comparison to placebo at a 2-sided 0.025 significance level to detect a treatment difference in maintenance EBS remission rate of 20% (40% on filgotinib and 20% on placebo).

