3.4. Examination of Subject Subgroups

Subgroup analyses for primary efficacy endpoint and adverse events are specified in Section 6.2.5 and Section 7.1.8, respectively.

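### The SAP tests each subgroup level on its own and plans no treatment-by-subgroup comparison, so nothing tests whether the effect differs between levels; where levels are clearly unequal in size, the separate p-values will often mislead

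*SAP*

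**What the plan says.** SAP 3.4 gives the location of all subgroup methods: "Subgroup analyses for primary efficacy endpoint and adverse events are specified in Section 6.2.5 and Section 7.1.8, respectively". SAP 6.2.5 sets the scope: "The following subgroup analyses will be performed for the primary efficacy endpoints for each individual study". It then lists the stratification factors together with age, sex, race, region, hs-CRP, fecal calprotectin, disease duration, disease activity and, for Cohort B and Maintenance, biologic history.

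The method takes two sentences. The first is "Non-stratified risk difference between treatment groups will be evaluated for each of the subgroups using" Fisher's exact test. The second is "A forest plot will graphically present the non-stratified risk difference and 95% CI using normal approximation with a continuity correction", one interval for each subgroup. No interaction, homogeneity or Breslow-Day test appears in the SAP or the protocol.

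Section 6.2.5 gives no significance level for these p-values, no descriptive or exploratory label, and no rule for reading them. Other sections do give such a label. SAP 6.4 calls its testing exploratory, SAP 6.4.2.1 calls its p-values nominal, and SAP 7.1.6 says no formal testing is planned for adverse events. The multiplicity scheme in SAP 3.5 covers only the primary and key secondary hypotheses.

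**The concern.** A p-value computed inside one level asks whether that level alone has enough subjects and enough effect to exclude no difference. A subgroup analysis asks whether the effect differs between levels. The plan tests the first question many times and never tests the second.

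The consequence depends on size. If the true effect is the same everywhere, a large level will tend to give a small p-value and a small level will not. Placed side by side, the two look like an effect that is present in one group and absent in the other. Conversely, if the effect really does differ, separate p-values are not a valid check of that. What is at stake is how consistency of effect is described in the report. The primary test, its alpha and the analysis sets are unaffected.

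**Working it through.** **Inputs (SAP 1.3).** Induction: "A sample size of 130 subjects in the placebo group and 260 subjects in each filgotinib dose (200 mg or 100 mg) group", with assumed rates of 25% and 10%; this "will provide 90% power for each filgotinib dose group comparison to placebo at a 2-sided 0.025 significance level". Maintenance: "A sample size of 95 subjects in the placebo group and 190 subjects in the filgotinib group", with assumed rates of 40% and 20% and stated power above 85% at the same level.

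**Reproducing the plan's power.** Continuity-corrected two-proportion formula: power = Φ{[|p1 − p2| − ½(1/n1 + 1/n2) − z·√(p̄(1 − p̄)(1/n1 + 1/n2))] / √(p1(1 − p1)/n1 + p2(1 − p2)/n2)}, with z = 2.241 for a two-sided 0.025.

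- Induction: p̄ = (13 + 65)/390 = 0.20. The numerator is 0.15 − 0.0058 − 2.241 × 0.0430 = 0.0479 and the denominator is 0.0376. Φ(1.27) = 89.9%, against a stated 90%.
- Maintenance: the same formula gives 86.3%, against a stated figure of more than 85%.

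Both figures reproduce, so the planning inputs are understood correctly.

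**Separate Fisher tests under an identical effect.** The documents give no subgroup sizes, so the share in the smaller level is an assumption and is varied from 10% to 50%. Power is exact (full enumeration of both binomials, two-sided 0.05). The two levels share no subjects, so P(larger significant, smaller not) = power(larger) × [1 − power(smaller)].

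| Study | Share in smaller level | Power, smaller | Power, larger | Larger significant, smaller not |
|---|---|---|---|---|
| Induction | 10% | 10% | 94% | 84.5% |
| Induction | 20% | 27% | 90% | 66% |
| Induction | 30% | 45% | 86% | 47% |
| Induction | 40% | 61% | 79% | 31% |
| Induction | 50% | 70% | 70% | 21% |
| Maintenance | 10% | 11% | 90% | 80% |
| Maintenance | 20% | 28% | 87% | 63% |
| Maintenance | 30% | 42% | 80% | 46% |
| Maintenance | 40% | 56% | 75% | 33% |

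Example, induction at 20%: 0.902 × (1 − 0.267) = 0.66. At an even split the 21% applies in each direction, so 42% of trials show one significant and one non-significant level.

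**Where this stops being the usual result.** In induction the probability is 52% with 36 of 130 placebo subjects in the smaller level (28%) and 49% with 38 (29%). In Maintenance it is 51% with 25 of 95 (26%) and 49% with 26 (27%).

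**Homogeneity test, same conditions.** The test is z = difference between the two risk differences, divided by its standard error, at two-sided 0.05. Simulation under the identical induction effect gives a false signal in 5.6% of trials (20% share) and 6.4% (10% share) with the unadjusted variance. With an adjusted-proportion variance the figures are 3.7% and 2.8%. Hence about 3 to 6%.

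**Power of that test.** Suppose the effect is wholly absent in the smaller level (10% against 10%) and as planned in the larger. The test then detects this in about 38 to 45% of trials at 20/80 and 17 to 30% at 10/90. The range reflects the choice of variance.

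**Number of comparisons.** Levels listed in SAP 6.2.5: Cohort A 4 + 20 = 24; Cohort B 6 + 20 + 14 = 40; Maintenance 6 + 20 + 14 = 40. Then 104 × 2 doses = 208. This is an upper bound, because US/Korea males who are not dual refractory are not randomised to 200 mg (SAP 1.2.1 and 6.2.4.4), so that level has no 200 mg comparison.

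**The case against.** The strongest reply is that the forest plot already shows an estimate and interval for every level, which is the right display for comparing effects, and that the SAP attaches no alpha, claim or decision rule to the subgroup p-values. Much of this stands. Fisher's test is not the only tool in the plan, and a misleading conclusion needs a reader to misuse p-values the SAP does not say how to read. But the plot is not a test of heterogeneity. Read by whether intervals cross zero, it repeats the problem: at a 20% share the larger level's interval excludes zero and the smaller one's does not in 59% (induction) and 61% (Maintenance) of trials.

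Three stronger readings are tempting and not supported.

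- A reader might infer that an identical effect will usually look absent in the smaller level whatever the factor. That fails above a share of about 26 to 28%, and the split of factors such as sex, disease activity or hs-CRP cannot be known from the documents.
- A reader might infer that the listed subgroups are known to be unequal, or are central to labelling. The documents state neither.
- A reader might take the 3 to 6% as evidence that a homogeneity test is better. Any valid 5% test gives about 5% when the effects are equal; the figure shows only that such a test does not respond to level size.

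It is also fair to object that the replacement is weak. At the very splits where separate p-values mislead most, a homogeneity test will miss a complete absence of effect in more than half of trials. That is a reason to call the result descriptive. It is not a reason to rely on p-values that answer another question.

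**Conclusion.** The concern holds in limited form. SAP 6.2.5 supplies within-level Fisher p-values and a forest plot, but no test of whether the effect differs between levels, and it does not say how the p-values are to be read. With the planned effect identical in both levels, the larger is significant and the smaller is not in about 21% to 85% of induction trials and 33% to 80% of Maintenance trials (shares of 10% to 50% and 10% to 40% respectively). It is the majority outcome only when the smaller level holds less than about 28% (induction) or 26% (Maintenance). These figures rest on the SAP 1.3 rates and sizes, 2:1 allocation within each level, a 0.05 reading of each p-value, and assumed subgroup shares. No confirmatory conclusion is affected, so this is a worthwhile improvement in reporting and not a flaw in the primary analysis.

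**What to change.** In SAP 6.2.5:

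- Keep the risk difference and 95% CI for each level.
- Drop the within-level Fisher p-values, or label them descriptive.
- Add one treatment-by-subgroup result per factor and dose: a homogeneity test on the risk difference, with its variance named in advance, or a logistic interaction term. Label it descriptive and unadjusted for multiplicity.
- State that a non-significant result is not evidence of a consistent effect, and cite the low power shown above.
- Where a level has no subjects in one arm, such as US/Korea males who are not dual refractory on 200 mg, show counts only.

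The cost is a few sentences of SAP text and one extra column in the forest plots. No new data are needed, and the primary analysis and alpha do not change. SAP Section 1 already provides for changes after finalization to be documented in the clinical study report. The downside is the low power of the added test, so it can inform the reading of the forest plot but cannot settle whether the effect is consistent.
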